### **General Procedure for Both Groups**

At any time in the study the use of further treatment including loop diuretics, aldosterone antagonists, morphine or other drugs or non-pharmacological therapies (including non-invasive ventilation) will always be dependent on the clinical conditions and will be at the discretion of the treating physician.

Non-invasive hemodynamic monitoring will be performed every 10 to 30 minutes during the first hour, every 30 to 90 minutes in the second to the fourth hour, and every 6 to 8 hours for the rest of the hospitalization as currently in practice at the enrolling institutions. Continuous recording of a three-channel ECG and transdermal oxygen saturation provided by automated monitoring systems will be applied as clinically indicated.

At the time of initial presentation and before discharge the patient leg circumference will be measured at three distinct points on either side: 10 cm distal from the caput fibulae, 5 cm above the ankles and at the middle of the metatarsi. The points of measurement will be marked. A special tape measure incorporating a spring exercising constant tension will be used ensuring a measurement independent of the strain applied by the investigator. Simultaneously and when possible, the central venous pressure will be obtained with a high resolution ultrasound imaging device combined with a translucent pressure manometer.

In addition, 15 ml of serum, EDTA plasma and urine will be collected at five time points (at baseline, at day 1, day 2, day 6 and discharge) for the measurement of biomarkers such as BNP, NT-proBNP, mid-regional pro-atrial natriuretic peptide, pro-adrenomedullin, copeptin, N-GAL, Cystatin C, Troponin T, and pro-endothelin that also reflect the response to treatment. The determination of NT-proBNP, mid-regional pro-atrial natriuretic peptide, pro-adrenomedullin, copeptin, N-GAL, Cystatin C, Troponin T, and pro-endothelin and pro-endothelin will be performed collectively after hospital discharge of patients and has no effect on patient treatment.

Transthoracic echocardiography (TTE) for the detailed assessment of systolic, diastolic, and valvular function will be performed as clinically indicated in the majority of patients. Response to therapy will be documented by daily clinical patient assessment using a predefined questionnaire as well as a visual analogue scale to record subjective course of dyspnea. Periodical measurements of electrolytes (sodium, potassium) and creatinine at study inclusion, every 24 to 72 hours during the first week and at discharge will be accomplished.

In the further course of treatment (usually one or two days before discharge), a beta-blocker will be added to this therapy at very low dose. Augmentation of the beta-blocker dosage will only be performed after discharge during the outpatient phase. Spironolactone (an aldosteron-receptor-antagonist) may be added in patients who remain in NYHA classes III and IV and in patients with low potassium concentration at presentation, as long as they have a serum creatinine below 150 µmol/l.

Despite early blood pressure intervention in the study group, special attention will be given to the final drug-treatment in both study groups. As ACE-inhibitors / ARB and beta-blockers provide the best documented survival benefit in patients with HF (3,7), initiation of a beta-blocker before hospital discharge will be strongly endorsed, and treatment of an equal percentage of patients in both arms with these two agents remains crucial.

### **Patient-assessed Dyspnea**

In order to assess the subjective sensation of dyspnea in the different treatment arms, patients will undergo a specific dyspnea test using a questionnaire and a visual analogue scale (VAS) according to the newest expert recommendations (41). This test will be performed at randomization, after 24 hours of treatment and prior to discharge. First, in sitting position (60°), patients will be asked how short of breath (SOB) they feel. There will be five different possible categories, reaching from “I am not SOB” to “I am severely SOB”. Afterwards, patients will be asked to draw a line on a VAS reaching from “I am not breathless at all” to “I am the most breathless I have ever been” indicating their subjective dyspnea. Afterwards, patients will be placed in laying position (20°) for three minutes and again subjective sensation of dyspnea using the above mentioned questionnaire as well as the VAS will be assessed. The difference in the VAS values between sitting (60°) and laying (20°) position will be documented. Furthermore, patients have to classify the difference in SOB lying down compared to sitting up using four categories reaching from “no difference” to “markedly worse”.

### **Questionnaire**

In order to estimate the possible effects of this open labelled study on patients' subjective outcome, a questionnaire is carried out at day 6 and discharge, respectively. It aims to assess to what extent the patient recalls in which study group he/she was enrolled in.

### **Discharge**

To minimize the effects of conditions unrelated to the acute HF episode on the length of hospital stay, a dedicated discharge protocol has been implemented in the months preceding this study. This interdisciplinary protocol was designed to optimize the transition from hospital to outpatient care. In addition, the protocol will help reduce the effects of treatment of co-morbidities and social issues related to placement of patients after discharge on the non-medical on the duration of hospitalization. To provide an objective measurement of physical performance permitting discharge, we will assess the ability of the patient to cover a simple standardized walking distance

on the ward without being limited by dyspnea. This walking test will in general be performed at day six after study inclusion.

Identical detailed discharge instructions (instructions and written instructions and / or educational material) including information about levels of activity, diet, discharge medication, follow-up appointment, weight monitoring, and what to do if symptoms worsen will be given in both groups.

### **Follow up**

90 days, 180 days and 360 days after hospital discharge, patients would be contacted by telephone and re-hospitalization, current medication, NYHA-classification as well as mortality if occurred would be documented. Further quality of life will be questioned using the Kansas City Cardiomyopathy Questionnaire (KCCQ) and the EQ-5D index (EuroQol group) during initial hospitalization and after 180 days. The KCCQ is a disease specific questionnaire designed to measure the effects of HF and treatments for HF on an individual's quality of life. The EQ-5D is a generic questionnaire, applicable to a wide range of health conditions and treatment, providing a simple descriptive profile and an index value for health status.

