Recent evidence from pilot studies for a long-term benefit of early aggressive therapeutic intervention in acute HF and the promising results obtained by vasodilatation with nitrates and hydralazine in chronic HF provide the rationale for our hypothesis that an early goal-directed decrement of preload and afterload with a target systolic blood pressure of 90 mm Hg to 110 mm Hg by aggressive vasodilatation in patients with acute HF in the non-ICU setting is safe, and leads to a better clinical and economical outcome. The early goal directed therapy as implemented by our protocol is expected to result in a more rapid resolution of symptoms, reduced time to discharge and reduced disease severity at the time of discharge. In addition, patients in the intervention group will receive a significantly higher dose of disease-modifying drugs like ACE-inhibitors and ARBs at the time of discharge. The difference in the dose of ACE-inhibitors and ARBs between both groups is expected to prevail within the first months of follow-up. The combination of both, improved disease state at discharge and higher doses of disease-modifying drugs during most of the study period is expected to result in a significant improvement in patient morbidity and mortality (11,28). This project is well in line with our previous research in this setting (10,29–31).

**Figure 3:** Theoretical model of expected effects of two different treatment strategies on quantitative markers of HF (B-type natriuretic peptide (BNP) or pulmonary capillary wedge pressure (PCWP)). Due to the aggressive preload and afterload decrement especially during the first 48 h of early goal directed treatment therapy, B-type natriuretic peptide and pulmonary capillary wedge pressure are expected to decrease faster and more pronounced than in the standard of care group.

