### 2.1 Primary Endpoints

- Death or HF re-hospitalization at 180 days.

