## **9. Study Schedule**

- Recruitment of first patient: November 10th, 2007
- Recruitment of last patient: if n = 770
- 180 day follow up complete: n = 770 + 180 days
- 360 day follow up complete: n = 770 + 360 days (last visit last subject)
- Main manuscript submission: n = 770 + 540 days

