## 2. Study objectives

### a. Primary objective

The aim of our study is to determine the safety and efficacy of an early goal-directed preload and afterload decrement with a target systolic blood pressure of 90 mmHg to 110 mmHg by aggressive vasodilatation versus standard medical care in a non-ICU setting in patients with acute HF. The primary endpoint is **death or heart failure re-hospitalization** up-to 180 days of follow-up.

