### b. Secondary objectives

Secondary endpoints are:

- All-cause mortality at 180 days.
- HF re-hospitalization at 180 days.
- Death or re-hospitalization from all causes at 180 days.
- Need for ICU admission during initial hospitalization.
- Acute coronary syndrome during initial hospitalization.
- Symptomatic hypotension during initial hospitalization.
- B-type natriuretic peptide (BNP) and creatinine level at 48 h and at discharge.
- Changes in circumferences of both legs and central venous pressure during hospitalization.
- Change in patient-assessed dyspnea at 48 h and prior to discharge.
- Blood pressure course over the first 6 days.
- Time to disappearance of a third heart sound (if present initially).
- Time to discharge.
- In-hospital days for HF at 180 days and 360 days.
- Total treatment cost at 180 days and 360 days.
- Functional status at 180 days and 360 days.
- Quality of life (EQ-5D-3L) at 180 days and 360 days.
- Fractures due to falls within 180 days and 360 days.
- Death or HF re-hospitalization at 360 days.

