## 11. Evaluation of safety parameters

### ff. Adverse events

Specific adverse events (AE) will be documented and investigated only during the course of

	Intervention arm (N=)	Standard of care arm (N=)
--	--------------------------	------------------------------

---

the index hospitalization (see “11.1.1.Brief summary of adverse events”). Additionally, during the first 180 days, all serious adverse events (SAEs) as defined by current Good Clinical Practice standards will be collected, fully investigated and documented in source documents and case report forms (CRF). Study duration encompasses the time from when the participant signs the informed consent until the last protocol-specific procedure has been completed (last FU at 360 days).

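### In-hospital harms are counted only until discharge, which the treatment is expected to bring forward, and are compared by tests that ignore days observed

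*Combined protocol and SAP*

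**What the plan says.** **In-hospital windows.** Protocol 2.2 and SAP 2.2 (b. Secondary objectives) list "Need for ICU admission during initial hospitalization", and define acute coronary syndrome and symptomatic hypotension over the same stay. SAP 11.1 (ff. Adverse events) states that specific adverse events "will be documented and investigated only during the course of" the index hospitalization. The list in SAP 11.1.1 includes falls, creatinine rise, hyperkalemia, systolic hypotension, acute coronary syndrome and ICU transfer.

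**Tests.** SAP 10.2.1 compares binary data by Fisher's exact test. SAP 11.1.3 compares adverse events per patient by chi-square. Its safety-population tally stops at the last confirmed intake of study drug, which is not a fixed window either. SAP 10.1.2 says that secondary endpoints follow the primary-endpoint approach, and Table 3 has a hazard-ratio column, so the method for the three in-hospital endpoints is not settled.

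**Expected effect on stay.** Protocol 1 (Introduction) says that the intervention is "expected to result in a more rapid resolution of symptoms, reduced time to discharge and reduced disease severity at the time of discharge". Time to discharge is itself a secondary endpoint.

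**Fixed windows already present.** Serious adverse events are collected over the first 180 days (SAP 11.1). Blood pressure is followed over 6 days, and BNP, creatinine and dyspnea have a 48 h reading.

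**Time origin.** The primary endpoint is "Death or HF re-hospitalization at 180 days" in protocol 2.1 and runs "up-to 180 days of follow-up" in SAP 2.1. Neither names day 0. Protocol 5 (Follow up) times the calls from discharge: "90 days, 180 days and 360 days after hospital discharge, patients would be contacted by telephone". Protocol 9 has "180 day follow up complete: n = 770 + 180 days", counted from recruitment. SAP 10.2.4 counts days from baseline.

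**The concern.** Safety is part of the stated hypothesis and of the primary objective in SAP 2.1, and protocol 6 names hypotension and reduced organ blood flow as the main expected harm. The events that would show this harm are counted over a window that closes at discharge. If treatment shortens the stay, intervention patients are watched for fewer days, and a test on patients or events does not allow for that. The arm could look safer with no difference in risk on any given day.

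The window also closes on a period in which the arms are expected to differ. Protocol 1 anticipates higher ACE-inhibitor and ARB doses at discharge in the intervention arm, with the difference lasting into the first months. Non-serious hypotension, creatinine rise or hyperkalemia after discharge is outside the adverse event window.

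**Working it through.** **Inputs.** The plan states no figure for this point, so there is none to reproduce. The documents give the direction (earlier discharge), the window (index stay), the tests and 385 patients per arm. The sample size does not depend on the window. Length of stay, event risk and hazard shape are assumptions.

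**1. Constant daily hazard, equal in both arms.** With control risk p over a 10-day stay, h = −ln(1 − p)/10. The intervention-arm risk over L days is 1 − exp(−hL).

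For p = 10% and L = 8: h = 0.10536/10 = 0.010536, risk = 1 − exp(−0.0843) = 8.08%, risk ratio 0.808.

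| Control risk (10 days) | 9 days | 8 days | 7 days |
|---|---|---|---|
| 5% | 4.51% (0.902) | 4.02% (0.804) | 3.53% (0.705) |
| 10% | 9.05% (0.905) | 8.08% (0.808) | 7.11% (0.711) |
| 20% | 18.19% (0.910) | 16.35% (0.817) | 14.46% (0.723) |

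Risk ratios are in brackets. The true ratio is 1.00 throughout.

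**2. Hazard concentrated early.** If the hazard halves every two days, the cumulative hazard to day 8 relative to day 10 is (1 − 2⁻⁴)/(1 − 2⁻⁵) = 0.9375/0.96875 = 0.968. With p = 10%, risk = 1 − 0.9^0.968 = 9.69%, risk ratio 0.97.

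**3. Longer stay.** At constant hazard, 12 versus 10 days gives 1 − 0.9^1.2 = 11.88%, risk ratio 1.19.

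**4. Chance of a nominal finding.** This uses 385 per arm, a normal approximation and two-sided 5%, for a result favouring the intervention when there is no true effect. Under a common window it is 2.5%.
- Constant hazard, 10% versus 8.08%: SE = √[(0.09 + 0.0743)/385] = 0.0207, z = 0.0192/0.0207 = 0.93, probability about 15%. At control risks of 5% and 20% it is about 10% and 26%.
- Halving hazard, 10% versus 9.69%: SE = 0.0215, z = 0.0031/0.0215 = 0.14, probability about 3.5%.

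Fisher's exact test is somewhat more conservative than this approximation.

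**5. What a per-day rate does.** Dividing by days in hospital removes the artefact when the hazard is flat. In step 2 it overcorrects: 0.968 × 10/8 = 1.21. The crude count and the per-day rate therefore belong side by side, together with a fixed early window.

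**6. Primary endpoint, on the least favourable reading.** Suppose the 180 days ran from discharge. Cumulative risk from randomization is then 1 − exp(−h(180 + L)). With 40% risk at 180 days, h = −ln(0.6)/180 = 0.00284, so stays of 10 and 8 days give 41.68% and 41.35%, a difference of 0.33 points. Over 30–45% risk and stays of 10 versus 7–9 days, the difference is 0.14–0.53 points (ratio 0.987–0.996).

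**The case against.** **Harms may fall in days that both arms share.** Hydralazine stops at 48 h, nitrates are reduced from day 3 with no entries in Figure 5a by day 6, and the discharge walking test is generally at day six. This stands as to size and is why step 2 belongs beside step 1. It does not remove the problem, because ACE-inhibitor and ARB titration continues to day 7.

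**The safety comparison is partly protected.** Serious adverse events run over 180 days, fractures due to falls are counted to 180 and 360 days, and study medication is given only in hospital, so the index stay is also the exposure window. SAP 6.6.4 calls secondary analyses explorative. All of this limits the consequence. It does not make the remaining in-hospital comparisons like for like.

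**Cox regression may be intended.** A reader could take SAP 10.1.2 and Table 3 that way. Time at risk would then be allowed for, but discharge would act as censoring that depends on treatment and prognosis.

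Two stronger readings are tempting and are not supported:

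- *That the primary endpoint clock starts at discharge, so that in-hospital deaths are lost.* The Follow up section only times the calls. Protocol 9 counts from recruitment and SAP 10.2.4 from baseline. SAP 4.2 checks that events are dated on or after randomization, and SAP 5.3 analyses all patients randomized. A call 180 days after discharge also covers day 180 from randomization.
- *That BNP and creatinine at discharge are the wrong comparison.* Severity at discharge is the stated hypothesis, and a 48 h reading exists. An earlier sample also leaves BNP less time to fall, which could work against the intervention.

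**Conclusion.** The concern holds for the in-hospital endpoints and the adverse events collected only during the index stay. As written, the arms are compared over periods that the treatment is expected to make unequal, and the tests make no allowance for it. For 8 versus 10 days and 10% control risk, the spurious risk ratio lies between about 0.81 (constant hazard) and 0.97 (hazard halving every two days). These are illustrations on assumed inputs, not forecasts. With equal stays there is no bias, and with a longer intervention stay it reverses.

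For the primary endpoint there is only an unstated day 0 and passages that should agree. Even the discharge-clock reading moves risk by about 0.1–0.5 points under the assumptions above. The change is worth making because it costs little and protects a safety conclusion that the trial sets out to draw.

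**What to change.** In SAP 10 and 11:

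1. Report ICU admission, acute coronary syndrome, symptomatic hypotension and the listed adverse events as rates per patient-day in hospital, beside the counts.
2. Add a comparison over a fixed window from randomization. For events recorded only in hospital, ICU admission included, use an early window such as to day 6. For acute coronary syndrome, use a longer window such as 30 days, drawing on the serious adverse event and rehospitalization data. The listed SAE categories have no ICU item, so a 30-day ICU endpoint is not clearly covered by the data collected.
3. Keep the counts during initial hospitalization as a supporting display, and state which test applies to each endpoint.
4. Show day-6 BNP and creatinine beside the discharge values, not in place of them. Day-6 samples are planned in both arms, and creatinine is measured every 24 to 72 hours in the first week.
5. As a clarification, state randomization as day 0 for all 180- and 360-day endpoints, and reconcile protocol 5 (Follow up), protocol 9 and SAP 10.2.4.

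The cost is SAP wording, a little more analysis and a second display. Sample size is unchanged. One limit remains: patients discharged before day 6 are still observed for less than the early window, so report their number by arm.

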### **Biobank**

Blood and urine samples are cryogenic stored (biobank) for up to ten years at a specific location at the University Hospital of Basel to analysis of emergent biomarkers associated with decompensated heart failure. All information are stored in order to protect from unauthorized access, loss, destruction and transformation. All samples are stored in a reversible anonym way. The biobank follows the OECD guidelines in order to guarantee protection in the process of sample submission and sample storage. Access to the samples is strictly restricted to the members of the research group. There are special regulations concerning the extraction, storage and use of human biological material (biobank reglament).

The samples are shipped in dry ice by specialized shipment company. Sample and data are anonymized before the shipment. Patients are informed about the existence and location of the biobank, the reasons of the storage and for how long the sample will be stored. Patients are informed about their right to request the destruction of the stored sample without giving any reason.

Every transfer has to be regulated by a Material Transfer Agreement and documented.

## **6. Risks and Benefits**

Early goal-directed preload and afterload decrement by aggressive vasodilatation with a target systolic blood pressure of 90 mm Hg to 110 mm Hg by using a fix therapy schedule has the potential to achieve faster cardiac re-compensation without jeopardizing major organ blood supply. Therapy with nitrates in dosages known to decrease preload and afterload in acute HF has been tested in two clinical trials and found to be superior to low dose nitrates in patients treated in mobile ICU. However,

the main potential adverse event induced by aggressive vasodilatation is arterial hypotension and consecutive decrement in renal and other major organ blood flow. Data from the A-HeFT study assure that the risk for an aggravation of a preexisting arterial hypotension (systolic blood pressure below 110 mm Hg) in therapy with nitrates and hydralazine is low, and that also patients with preexisting arterial hypotension will benefit from this therapy option (44). It is the concept of this study that the clinical hemodynamic monitoring available in the emergency department (first 24 hours) and general medical ward (second 24 hours and remaining hospitalization) allows the judicious use of this fix therapy schedule to achieve requested vasodilatation and the target blood pressure. It is important to note that in case of symptomatic arterial hypotension easy applicable measures to increase blood pressure are available. A major advantage of the transdermal application form of nitrates during the initial part of the study is the option to stop drug resorption by removing the patch.

During the first 48 hours patients would be encouraged to perform gymnastics of their calves before standing up and leave their beds only in company of the responsible nurse, in order to avoid symptoms of orthostatic hypotension. In case of headache, which is a common side effect in nitrate therapy, treatment would be effectuated with paracetamol (e. g. Perfalgan®) 1 g intravenous.

In order to avoid a possible “steal phenomenon” of hydralazine, patients with evidence for an acute coronary syndrome will be treated only with nitrates and will not receive hydralazine.

For routine clinical monitoring withdrawal of blood specimen will be necessary. This is associated with a minimal residual risks associated with peripheral venipuncture including hematoma, bruising, and skin infection that is unrelated to this study as it is clinically indicated. All patients can expect to receive superior patient care as compared with patients not entered in this trial. In addition, on the long-term, patients themselves may benefit from improvement in treatment options documented in this study. HF is characterized by recurrent decompensations. Therefore, chances are high, that the insight gained by this study will be available for the clinical care of the majority of patients during their next episode of decompensation.

